4.1 General Design

This cluster-randomized trial will be conducted with 14 Philadelphia CMHCs, 7 randomized to ATTOC and 7 to usual care (UC). Following randomization, study staff will visit sites to recruit clinic personnel and clients over a 4 to 6 week period. Those eligible will complete informed consent and HIPAA forms and a baseline assessment to establish pre-intervention levels on all measures (baseline). After 4-6 weeks, the ATTOC intervention will be implemented over 9 months, from Week 1 to Week 36 (with UC at the control sites). Two mid-intervention assessments (Weeks 12 and 24) will allow for performance feedback (see Outcomes Data) and mediational analyses. Week 36 (end-of-treatment; EOT) and 52 (3-months post-EOT) assessments will allow for evaluation of changes on outcomes between groups over time. All measures will be conducted at the respective CMHC

(or over the phone if necessary) and 7-day point prevalence smoking cessation will be verified using a breath carbon monoxide (CO) monitor (abstinence = < 8ppm; [93]). Figure 1 illustrates the study design.

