Once sites are randomized, we will use a 4 to 6 week window for subject recruitment. This will allow study staff to recruit in-person for multiple days and across several weeks to ensure that we access all site personnel and a representative sample of clients. We have experience recruiting in clinic settings [59, 71] and have 2 ongoing studies that follow such procedures (R01 CA165001; R01 DA033681). If the 4-6 week period is not sufficient time to recruit a participant sample, the Principal Investigator reserves the right to lengthen the recruitment window by 4-6 weeks. The Principal Investigator may also need to under-enroll clinic personnel or client participant groups at certain sites due to organizational constraints. This under-enrollment will be supplemented at larger clinics by over-enrolling participants at other sites. In order to prevent possible retribution against clinic

personnel on the part of clinic leadership, we will not disclose the enrollment decisions of clinic personnel, and we will offer smoking cessation resources to the clinic.

To recruit personnel, we will use staff meetings, electronic and written communication, and hold study-specific meetings. To recruit clients, as done now (R01 CA126969), but modified as needed upon advice from the Community Advisory Council, our Research Assistants (RAs) will assess every scheduled client for interest and eligibility using clinic schedules to approach clients prior to or after appointments. We post program flyers and brochures in clinics as well. Participants who are eligible and interested in the study will be scheduled for an intake session. To assess external validity, eligible personnel and clients who refuse entry will be compared to those who enroll based on available data (e.g., smoking status, years employed, nature of SMI).

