6.4 Subject Withdrawal

Clinic personnel or client participants may choose to withdraw from the study at any time. They do this by providing verbal or written communication to this effect. Withdrawal from the study will not impact employment status (clinic personnel) or access to care (clinic clients) within the clinic. The Principal Investigator may withdraw subjects who violate the study plan, to protect the subject for reasons related to safety or for administrative reasons. It will be documented whether or not each subject completes the study. Subjects who withdraw early will be contacted to complete a final visit (Week 52) to collect final evaluations and assess adverse events.

To increase retention and adherence we will: 1) conduct interventions at the clinic; 2) conduct assessments during scheduled clinic visits or by phone; and 3) as is standard in TUD trials [65, 66], provide financial compensation for assessment completion. Although we expect that a small percentage of personnel and clients will leave their agencies, based on our past trials [71] and preliminary research with DoH clinicians [19], we expect that <15% of personnel and clients will withdraw from the trial or be lost-to-follow-up and ~85% of assessments will be completed, which exceeds past trials (e.g., [102]). As is advised in smoking cessation trials [101], intent-to-treat (ITT) will be used for Aim 2. Should, in the unlikely event, a CMHC withdraw from the trial, our time-line and prospective recruitment will allow replacement with a new CMHC.

7 Statistical Plan

All data are maintained on password-protected computers within a DMS that uses ORACLE and MS ACCESS to permit web-based real-time data entry, storage, and QA

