7.2 Statistical Methods

We will assess sample characteristics by treatment arm and site with chi-square or regression. These variables will also be examined for their relationship to completion of outcomes. Variables related to treatment arm or completion of follow-ups ($p < .10$) may be covariates in analyses. Fidelity and adherence measures will be evaluated across treatment arms, and the measures can be included in primary analyses. We will examine if the rate of missing data is related to a range of variables using chi-square and regression and use appropriate methods for dealing with missing data (e.g., [115]). Analyses will assume that all subjects for whom smoking outcome data are unavailable are smokers (ITT) but we can also conduct a "completers-only" analysis. Because this is a cluster-randomized trial, the observations within a cluster cannot be considered totally independent. Variation among clusters may be confounded with treatment because clusters are nested within treatment. We will account for this clustering using hierarchical linear models (mixed models), estimating separate variance components for random site effects within treatment. Lastly, since we cannot guarantee that clinicians will be blind to their clients enrolling in this study, we will include a statement in personnel consent forms asking that they refrain from asking their clients if they are enrolled in the study.

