8.1 Data Safety Monitoring Plan (DSMP)

For this study, we will use established PENN procedures and infrastructure for data and safety monitoring. During the course of the study, safety and data quality monitoring will be performed on an ongoing basis by the Principal Investigators and the study staff. Study staff members are responsible for collecting and recording all clinical data using the established MOP. This includes ensuring that all source documents exist for the data on the Case Report Forms, ensuring all fields are completed appropriately, and ensuring that all corrections are done according to Good Clinical Practice (GCP). Any inconsistencies/deviations will be documented. The study Key Personnel, which include physicians ([name]) and psychiatrists ([name]), will review data on an ongoing basis and will document reviews by initialing and dating reports. Study staff members conduct 100% quality assurance on data, comparing all hard copy data to computer files.

Staff training will consist of an explanation of the protocol and review of the Case Report Forms. In addition, the duties of each staff person will be outlined and all applicable regulations will be reviewed. Mock sessions with critical feedback will be conducted. The MOP will be used for staff training and to guide procedures throughout the trial. Senior personnel will supervise junior staff and provide re-training in the study protocol as needed. [name] will oversee the staff implementing the ATTOC intervention and Drs. [name] and [name] will oversee the staff handling recruitment and data collection and management.

Enrollment will be complete when 280 personnel and 700 clients are consented and complete the study. Monitoring days will be conducted periodically throughout the study. The monitoring is conducted by the PENN IRB and the PENN Office of Human Research (see www.med.upenn.edu/ohr). These audits are typically conducted annually and involve the review of regulatory documents, the ascertainment and documentation of informed consent, the compliance with the study protocols, and the completion of CRFs.

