Quality Assurance Procedures and Participant Confidentiality: All subjects will be screened for eligibility using formal study forms and the Principal Investigator will regularly audit accrual to ensure that participants meet eligibility criteria. In addition, the Study Coordinator will audit all study files to ensure that questionnaires completed by subjects contain all items. Lastly, to protect confidentiality, all data will be numerically coded and information linking the numeric code to the subject's name will be kept in a secured file cabinet and office. In addition, computer data files will be stored on password-protected computers and communication among the staff will use participant code numbers, not names. No information concerning data will be presented with participant names. Data will be collected in a private room or via telephone.

Undue Influence/Coercion and Enrollment Status: In order to protect personnel participants from possible undue influence and coercion regarding enrollment in our study, the voluntary nature of the study is stressed throughout the informed consent documents. With regard to clinic leadership, we assess their willingness to ensure that personnel employability will not be affected at the time of pre-enrollment (within the ORIC assessment), and we ask a designated clinic leader to sign an informed consent acknowledgement form. This document asks the clinic leader to acknowledge that s/he has read and approved the consent form and agrees on behalf of the clinic to reduce undue influence due to employability risks. This signed form will be presented to clinic personnel at the time of informed consent to address this potential concern. The consent will also state that the study team cannot conceal personnel enrollment decisions after the study treatment phase is initiated. If the clinic is disqualified during the enrollment period due to under-enrollment, personnel enrollment decisions will not be disclosed to clinic leadership.

Adverse Event Reporting: In accordance with NIH and IRB guidelines, this protocol will employ the following mechanisms for adverse event reporting: 1) alert the IRB of any and all reports of serious adverse events; 2) informing all members of the study team of any and all reports of serious adverse events; and 3) notification to NIH of any actions taken by the IRB with regard to data safety monitoring.

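### A randomised clinic that withdraws may be replaced, with no rule for allocating the replacement or keeping the departed clinic in the analysis; this can bias a comparison of 7 clinics per arm

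*Combined protocol and SAP*

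**What the plan says.** All references are to the combined protocol and SAP.

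- **Allocation.** Section 4.1 fixes 14 clinics, 7 per arm. Section 4.2 describes computerised assignment of eligible sites, matched on size and on organisational readiness (ORIC).
- **Order.** Recruitment follows randomisation (section 5.5): "Once sites are randomized, we will use a 4 to 6 week window for subject recruitment".
- **Withdrawal of a clinic** (section 6.4): "Should, in the unlikely event, a CMHC withdraw from the trial, our time-line and prospective recruitment will allow replacement with a new CMHC".
- **Disqualification** (section 10.2): "If the clinic is disqualified during the enrollment period due to under-enrollment, personnel enrollment decisions will not be disclosed to clinic leadership". Since enrolment follows randomisation, this too is removal after randomisation.
- **Under-enrolment** (section 5.5): the window may be lengthened by 4–6 weeks, and "This under-enrollment will be supplemented at larger clinics by over-enrolling participants at other sites".
- **Analysis population** (section 6.4): "intent-to-treat (ITT) will be used for Aim 2". Section 7.2 applies this to individuals, by counting missing smoking outcomes as smoking. No analysis population is stated for Aims 1 and 3, which are also primary.
- **Enrolment target** (section 8.1): "Enrollment will be complete when 280 personnel and 700 clients are consented and complete the study".

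**The concern.** Randomisation protects the comparison only if the clinics analysed in each arm are the clinics that were randomised to it. Here a clinic can leave after learning its arm, and the arms differ greatly in what they ask. ATTOC involves 10 sessions over 9 months, including a 3-day and a 2-day site visit, and a leadership group (sections 6.1.2, 6.2.1, 6.2.2 and 6.2.4). Usual care involves one training day. It is plausible, though not documented, that a clinic with low readiness would be more likely to leave the ATTOC arm.

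Sections 4.2 and 5.5 deliberately seek clinics that do not respond to the first invitation, so that low-readiness sites are represented. Replacing such a clinic with a more willing one would undo that. Clinics also start in waves (section 4.6), so a replacement would start later and possibly under different conditions, such as the COVID-19 procedures.

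With 7 clinics per arm, one clinic is 1/7, or 14%, of an arm.

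**Working it through.** **1. Reproduce the plan's detectable differences (section 7.1).**

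Aim 1 inputs: SD 0.87, 7 clinics per arm, m = 20 personnel per clinic (280/14), 80% power, two-sided alpha 0.05.

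Formula: difference = (t.975,12 + t.80,12) × SD × √(2·DE/(7m)), with DE = 1 + (m − 1)·ICC and 14 − 2 = 12 degrees of freedom.

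At ICC .10: DE = 2.9, and (2.179 + 0.873) × 0.87 × √(5.8/140) = 0.540.

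| ICC | 0 | .05 | .10 | .15 |
|---|---|---|---|---|
| Stated | 0.32 | 0.44 | 0.54 | 0.62 |
| Recomputed | 0.317 | 0.443 | 0.540 | 0.623 |

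The plan's figures with 15% individual loss (0.34/0.46/0.56/0.63) also reproduce, with m = 17: 0.344/0.462/0.555/0.635.

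For Aim 2 (control rate 2%, m = 50, pooled two-proportion formula, normal quantiles) the result is 4.2/10.0/14.9/19.4 points against the stated 4/10/15/19. The allowance for loss covers individuals only; none is made for loss of a clinic.

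**2. What it costs to lose one clinic and not replace it.**

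Aim 1, 7 v 6 clinics, 11 degrees of freedom: (2.201 + 0.876) × 0.87 × √(DE/(7m) + DE/(6m)). At ICC .10: 3.077 × 0.87 × √(2.9/140 + 2.9/120) = 0.567.

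| ICC | 0 | .05 | .10 | .15 |
|---|---|---|---|---|
| 7 v 7 | 0.317 | 0.443 | 0.540 | 0.623 |
| 7 v 6 | 0.333 | 0.465 | 0.567 | 0.653 |

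The increase is about 5% (0.567/0.540 = 1.05).

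Aim 2 at ICC .05, by the formula that reproduces the plan: 9.97 points becomes 10.41 if the lost clinic is in ATTOC (4%) and 10.73 if it is in usual care (8%). A stricter version with t quantiles and unpooled variance gives 11.05 becoming 12.32 (11%) or 11.38 (3%).

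These assume that the clinic contributes nothing. The cost is smaller if its participants are followed.

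**3. What substitution could do to Aim 1 (illustration; the assumptions are not in the documents).**

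Assume no true effect, m = 20, the ATTOC clinic with the lowest true clinic effect leaves, its data are excluded, and a randomly drawn clinic takes its place in that arm. The expected minimum of seven standard normal values is −1.352, and the substitute has expectation 0, so

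bias = 1.352 × SD × √ICC / 7.

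At ICC .10: 1.352 × 0.87 × 0.316 / 7 = 0.053. A simulation with 200,000 replicates agrees to within about 0.001 at each ICC and gives the error rates.

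| ICC | .05 | .10 | .15 |
|---|---|---|---|
| False ATTOC advantage (simulated) | 0.038 | 0.053 | 0.064 |
| As share of the stated detectable difference | 9% | 10% | 10% |
| False positives favouring ATTOC (nominal 2.5%) | 4.6% | 5.1% | 5.3% |

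If the departing clinic is chosen without regard to outcome, the simulated bias is 0.000 and the two-sided error stays at about 5%.

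**The case against.** The strongest reply is that the documents leave room for a sound procedure.

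- **Placement and exclusion.** A reader might infer that the departed clinic's data are dropped and the new clinic is put into the vacated arm, with its allocation known. Neither is stated. The only allocation procedure described is the computerised one in section 4.2. Section 6.4 asks participants who withdraw early to attend a final Week 52 visit, and section 7.2 counts missing smoking outcomes as smoking. This stands. Even so, a fixed 7:7 design, a promise of replacement and a target counted in completers make substitution the natural reading, and nothing rules it out.
- **Disqualified clinics.** A reader might infer that a clinic disqualified for under-enrolment is also replaced. Section 10.2 is a confidentiality sentence and does not say so; section 5.5 offers a longer window and over-enrolment elsewhere. This stands. What remains is that removal after randomisation is foreseen and not reconciled with section 5.5.
- **ITT.** Replacement does not contradict ITT, because a further clinic can be added while the first is retained. The two provisions are simply not reconciled at clinic level.
- **Direction of bias.** No clinic withdrawal rate or pattern is given, withdrawal is described as unlikely, clinics may receive up to $1,500 to offset staff time, and usual-care clinics could leave too. So bias is possible, not established.
- **Feasibility.** A clinic that leaves before enrolling anyone has no data to analyse. Phone contact cannot supply the breath CO that section 4.8.1 requires, so abstainers reached only by phone would count as smokers. Both points stand and limit the fix.

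**Conclusion.** The concern holds in a limited form. The plan permits replacement of a withdrawn randomised clinic, foresees disqualification after randomisation, and has no clinic-level rule for allocation of replacements or for the analysis population. That can bias the comparison if departure is related to arm and outcome; if departure is unrelated to outcome, it does not.

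The documents do not support saying that the plan does bias the result, nor any fixed percentage by which the effect would be overstated. The 0.038–0.064 points and the 4.6–5.3% error rate describe an assumed case in which the weakest ATTOC clinic leaves and its data are excluded. They show only that one substitution can matter with seven clinics per arm.

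The main concern is selection, not power: leaving a lost clinic unreplaced costs about 5% in the Aim 1 detectable difference. For Aim 2 the cost is 4–8% at ICC .05 by the plan's own formula, or up to 11% by the stricter one.

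**What to change.** Amend sections 6.4 and 7.2 to state that:

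1. Every randomised clinic is reported by arm, and all its enrolled personnel and clients are analysed in the assigned arm for Aims 1, 2 and 3.
2. After a clinic leaves, follow-up continues by phone or visit where participants agree. For Aim 2, missing smoking outcomes count as smoking, as section 7.2 already provides.
3. Any further clinic is an addition, not a substitute, and receives its own concealed random allocation under the section 4.2 procedure.
4. Clinics that leave or are disqualified before enrolling anyone are reported by arm, with the reason.
5. Sections 5.5, 6.4 and 10.2 are reconciled on what happens when a clinic under-enrols. A ban on all disqualification is not needed for this point.
6. For Aim 3, a sensitivity analysis omits the departed clinic, because dilution can favour a non-inferiority claim.

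The cost is mainly wording; phone assessment is already allowed (sections 6.3 and 6.4). The downsides are slight dilution of the effect if a clinic leaves, and possible departure from 7:7.

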7.1 Sample Size and Power Determination

For cluster-randomized designs, clinic is the unit of randomization and the unit of analysis is the individual. Power is reduced by variability among clinics, represented by the intra-class correlation (ICC), analogous to an R-squared. The size of the individual sample affects precision within clusters and certain outcomes are less susceptible to potential confounding vs. others (e.g., smoking rates vs. provider adherence) since they are more independent.

For Aim 1, the analysis will compare ATTOC to UC on weeks 36 (EOT) and 52 rates of adherence to guidelines for treating TUD. The sample size was determined by assessing the mean change in practice behavior detected in Guldish et al. [18]. Given the expectation from that trial that the UC mean level of practice will be 2.36 (SD=.87), the present sample of N=14 agencies (with 280 subjects) provides 80% power ($\alpha=.05$) to detect an effect if practice behavior increases by 0.32 (on a 5-point scale) if the ICC is 0. But if our ICC is .05, .10, or as high as .15, we have 80% power ($\alpha=.05$) to detect a difference between ATTOC and UC of 0.44, 0.54, and 0.62, respectively. If 15% of the personnel are lost-to-follow-up, we will have 80% power ($\alpha=.05$) to detect an effect if practice behavior increases by 0.34 for ICC=0, by 0.46 for ICC=.05, by 0.56 if ICC=0.10, and by 0.63 if ICC=.15. The effects of ATTOC were stronger at the 3-month follow-up (mean change of 0.51), vs. EOT [18], so the current power is adequate for both time-points. Likewise, because the client sample will be more than twice as large as the clinic staff sample, we will have greater than 80% power to detect differences using the measure of physician adherence collected from clients.

For Aim 2, the analysis will compare the rates of smoking cessation between the ATTOC intervention and UC at weeks 36 and 52. We can expect that UC cessation rate will be < 2% [18]. With 14 sites (n=700 clients, ITT), we have 80% power ($\alpha=.05$) to detect a difference between ATTOC and UC of 4% with an ICC=0. But if our ICC is .05, .10, or as high as .15, we have 80% power ($\alpha=.05$) to detect a difference between ATTOC and UC of 10%, 15%, and 19%, respectively, with 14 sites and n=700 client (ITT).

For Aim 3, the analysis will use non-inferiority testing to compare mental health and QOL across ATTOC and UC at weeks 36 and 52. Standard statistical tests, which may yield a non-significant comparison of means or proportions, cannot be used to claim that the treatments are equal since "the absence of evidence is not evidence of absence". Among persons with SMI, the rate of psychiatric hospitalization nationally is 11.4% [114], which may represent UC (i.e., 88.6% of UC subjects will not have a hospitalization across the 52 weeks). One study found that 3.3% of clients with an SMI treated for TUD had a psychiatric hospitalization [48] or that 96.7% of clients treated for TUD did not experience a psychiatric hospitalization. We assume 14 sites (700 clients), with potential loss of 15% to follow-up, and assume approximately 90% non-hospitalization in the UC group. We will set our non-inferiority floor 20% below the US rate, which yields 80% power to detect non-inferiority if the ICC is as much as 0.15 (more power if ICC is less than 0.015).

A trial with smokers with an SMI reported baseline BASIS-R scores of 2.1 (SD=0.8) and SF-12 scores of 48.7 (SD=12.5) for the physical sub-scale and 27.8 (SD=12.9) for the mental sub-scale, which estimates UC [107]. Given the sample of 14 sites (700

clients) and potential 15% loss to follow-up, we have 80% power ($\alpha=0.05$) to detect non-inferiority if the results for the ATTOC arm differ from UC by as much as 0.19 on the BASIS-R, when ICC=0, and by 0.50 when ICC=0.15.

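### The Aim 1 claim of adequate power at both time points does not follow from the plan's own figures: the cited 0.51 effect is below its 80%-power differences at ICC .10 and .15, and no effect is given for week 36

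*Combined protocol and SAP*

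**What the plan says.** Section 7.1 bases Aim 1 on an earlier study of the intervention. It expects that the "UC mean level of practice will be 2.36 (SD=.87") on a 5-point scale, and takes "the present sample of N=14 agencies (with 280 subjects") as the sample. With an ICC of 0 the detectable difference at 80% power is 0.32. At ICC .05, .10 and .15 the sample has 80% power "to detect a difference between ATTOC and UC of 0.44, 0.54, and 0.62, respectively". With 15% of personnel lost, the difference is 0.34 at ICC 0 and then rises "by 0.46 for ICC=.05, by 0.56 if ICC=0.10, and by 0.63 if ICC=.15".

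The section then reports that the earlier study found a stronger effect at its 3-month follow-up (mean change 0.51) than at end of treatment, and ends, "so the current power is adequate for both time-points". It gives no effect for end of treatment. Section 7.2.1 makes adherence at both week 36 (end of treatment) and week 52 primary.

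**The concern.** Two steps in the argument fail.

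- **Size.** The only effect offered in support, 0.51, is smaller than four of the six differences that the plan lists for a non-zero ICC. At ICC .10 and .15, the plan's own numbers put power at 0.51 below 80%.
- **Direction.** The 0.51 belongs to the time point with the stronger effect. Adequate power for the larger effect says nothing about the smaller one, and the section gives no week 36 value.

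Aim 1 is a primary aim with two primary time points. If its result is null, the reader needs to know how likely the trial was to detect an effect of the size it was planned around. An unconditional statement of adequacy gives too favourable an answer over part of the ICC range that the plan itself considers.

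**Working it through.** **Inputs.** From section 7.1: SD 0.87, 14 clinics, 280 personnel (280/14 = 20 per clinic), 15% loss (17 per clinic left), alpha .05, and ICC 0, .05, .10 and .15. From section 4.1: 7 clinics per arm. Section 7.1 does not state sidedness or the reference distribution; both were settled by finding what reproduces its figures.

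**Formula.** With m personnel per clinic,

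SE = 0.87 × √( 2[1 + (m − 1)ICC] / (7m) ),

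two-sided alpha .05, noncentral t on 14 − 2 = 12 df.

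Example for m = 20 and ICC .10: 1 + 19 × .10 = 2.9, so SE = 0.87 × √(5.8/140) = 0.177. The detectable difference is close to (2.179 + 0.873) × 0.177 = 0.540.

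**Step 1: reproduce the plan's detectable differences.**

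| ICC | Stated, no loss | Computed (m = 20) | Stated, 15% loss | Computed (m = 17) |
|---|---|---|---|---|
| 0 | 0.32 | 0.317 | 0.34 | 0.344 |
| .05 | 0.44 | 0.443 | 0.46 | 0.462 |
| .10 | 0.54 | 0.541 | 0.56 | 0.555 |
| .15 | 0.62 | 0.623 | 0.63 | 0.635 |

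All eight agree within .005. A two-sided normal calculation does not reproduce them: with no loss it gives 0.291, 0.407, 0.496 and 0.572.

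**Step 2: power at 0.51 by the same calculation.** For m = 20 and ICC .10 the noncentrality is 0.51/0.177 = 2.88.

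| ICC | t, 12 df, no loss | t, 12 df, 15% loss | Normal, no loss | Normal, 15% loss |
|---|---|---|---|---|
| 0 | 99% | 99% | >99% | 99% |
| .05 | 90% | 87% | 94% | 92% |
| .10 | 75% | 73% | 82% | 80% |
| .15 | 63% | 62% | 71% | 69% |

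Solving for the ICC at which power at 0.51 equals 80% on 12 df gives about .083 with no loss and about .075 after 15% loss.

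**Step 3: week 36.** The documents say only that the effect was smaller than at follow-up, so a range must be assumed. Power on 12 df with no loss:

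| Assumed effect | ICC .05 | ICC .10 | ICC .15 |
|---|---|---|---|
| 0.32 | 53% | 38% | 30% |
| 0.40 | 72% | 55% | 44% |
| 0.45 | 81% | 65% | 53% |

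These values illustrate the direction; none is an estimate of the earlier study's end-of-treatment effect.

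**Step 4: what 0.51 measures.** Section 2.1 describes the earlier study as non-randomized and single-arm, so 0.51 is a change within one group. Using it as the difference between arms assumes no change in usual care. Section 6.2.1 gives usual care personnel a 1-day training seminar in guideline treatment. Any improvement there reduces the contrast and the power in step 2.

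**The case against.** The plan hides nothing: it lists each detectable difference by ICC, with and without loss, just before the sentence, and presents .15 as the high end. At ICC 0 and .05 the claim holds for week 52 (99% and 90%; 99% and 87% after loss). Section 7.2.1 plans a z-score test, and a normal calculation reaches 82% at ICC .10, or 80% after loss. The arithmetic behind the listed differences is sound.

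All of this stands, and it narrows the point to one unqualified conclusion. It does not rescue that conclusion. The documents give no Aim 1 ICC estimate that would allow .10 and .15 to be set aside. The plan's listed differences match the 12-df calculation and not the normal one. Even the normal calculation falls short at ICC .15. None of these arguments supplies a week 36 effect.

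A reader might also infer that the next sentence, "we will have greater than 80% power to detect differences using the measure of physician adherence collected from clients", is wrong at high ICC. The documents do not support that. They give no SD, effect or ICC for the client measure, so putting 0.51 and 0.87 into it borrows staff values for a different instrument. The more natural reading applies the differences just listed to the larger client sample. With 50 clients per clinic and the same SD, power at 0.32, 0.44, 0.54 and 0.62 is 99%, 91%, 87% and 85% at ICC 0, .05, .10 and .15, so the sentence holds.

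Nor can one say that power reaches 80% only at an ICC near .05. Lower values do better, and the limit is about .075 to .083.

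**Conclusion.** The adequacy statement is unsupported as written. At week 52, for a between-arm difference of 0.51, power is at least 80% only if the ICC is about .075 or lower after 15% loss. At ICC .10 and .15 it is 73% and 62%. These figures assume SD 0.87, equal clinic sizes, 7 clinics per arm and a two-sided test on 12 df, and they take 0.51 as the full difference between arms. The shortfall at ICC .10 depends on the t reference distribution; the shortfall at ICC .15 does not.

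For week 36, the documents support only that power is lower than at week 52 for the same ICC and loss. How much lower cannot be said without the end-of-treatment effect. The design is not shown to be underpowered at every ICC, and the listed detectable differences need no correction.

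**What to change.** Replace the adequacy sentence in section 7.1 with:

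> At a difference of 0.51 (week 52), power after 15% loss is 87%, 73% and 62% at ICC .05, .10 and .15, and is at least 80% only if the ICC is about .075 or lower (about .083 with no loss). Power at week 36, where the effect in the earlier study was smaller, is lower.

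Then state the earlier study's end-of-treatment effect with its power at each ICC, and note that 0.51 is a single-arm change, so the figures assume no improvement in usual care. Leave the client-measure sentence as it is.

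The cost is a short text change and a less favourable statement of power. It needs no added participants and no change to the design or analysis.
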